**Contacts for SAE reporting are specified in Appendix 3.**

### **9.2.1 Immune-mediated Adverse Events**

Immune-mediated AEs are AEs consistent with an immune-mediated mechanism or immune-mediated component for which non-inflammatory etiologies (e.g. infection or tumor progression) have been ruled out. Immune-mediated AEs can include events with an alternate etiology which were exacerbated by the induction of autoimmunity. Information supporting the assessment will be collected on the subject's case report form.

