### 10.3 Statistical Analyses

#### 10.3.1 Safety Analyses

All recorded adverse events will be listed and tabulated by system organ class, preferred term, treatment and overall. Death will be listed and summarized. Any significant physical examination findings will be listed. ECG, vital signs and clinical laboratory test results and corresponding change from baseline values will be listed and summarized by treatment. Values for ECG, vital signs and clinical laboratory test results outside the pre-specified criteria will also be listed and summarized. ECG readings will be evaluated by the Investigator and abnormalities, if present, will be listed. Immune-related AEs will be listed and tabulated by system organ class, preferred term, treatment, overall and time points.

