- Drug-related adverse events on-treatment
- Adverse events on-treatment occurring in $\geq 5\%$ of subjects*
- Drug-related adverse events on-treatment occurring in $\geq 5\%$ of subjects*

* The 5% criterion cutoff refers to 5% in any column.

Two types of summaries are produced, one for subjects with grade 1-5 AEs and a second restricted to subjects with grade 3-4 & grade 5 AEs.

7.7.5 *Immune-Mediated Adverse Events*

In order to further characterize AEs of special clinical interest, an analysis of immune-mediated AEs (IMAEs) will be conducted. Immune-mediated AEs are specific events (or groups of PTs describing specific events) that include pneumonitis, diarrhea/colitis, hepatitis, nephritis/renal dysfunction, rash, endocrine (adrenal insufficiency, hypothyroidism/thyroiditis, hyperthyroidism, diabetes mellitus, and hypophysitis), and other specific events, considered potential immune-mediated events by investigator, that meet the definition summarized below:

- those occurring within 90 days of the dose,
- regardless of causality,
- treated with immune-modulating medication (of note, endocrine Adverse events such as adrenal insufficiency, hypothyroidism/thyroiditis, hyperthyroidism, diabetes mellitus, and hypophysitis are considered IMAEs regardless of immune-modulating medication use, since endocrine drug reactions are often managed without immune-modulating medication).

For the most recent immune-oncology studies, the data collection for IMAE was modified to also collect data on investigator assessment of potential IMAE including evidence of immune mediated etiology. For these studies, an additional criteria accounting for immune mediated etiology or immune mediated component is also to be considered:

- with no clear alternate etiology based on investigator assessment, or with an immune-mediated component

The list of MedDRA preferred terms used to identify Immune-Mediated adverse events is revisited quarterly and updated accordingly. The preferred terms used for the selection at the time of the database lock by categories will be provided.

IMAEs will be summarized by treatment group for each immune mediated category / PT using the 90-day safety window:

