- Overall summary of AEs (subjects with grade 1-5 AEs) presented by immune mediate Category / PT. This summary includes all AEs that are qualified for IMAE preferred terms list, without requirement of either usage of immune modulating medications or accounting for immune mediated etiology or immune mediated component.

- Overall summaries of IMAEs [(subjects with grade 1-5 AEs) and (restricted to subjects with grade 3-4 & grade 5 AEs)] where immune modulating medication was initiated presented by Category / PT.
- Overall summaries of endocrine IMAEs [(subject with grade 1-5 AEs) and (restricted to subjects with grade 3-4 & grade 5 AEs)] presented by Category / PT.

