APPENDIX 2 IMMUNE MEDIATED ADVERSE EVENTS DEFINITION AND CONVENTIONS

Immune-Mediated Adverse Event Definition

Category	Preferred Terms
ADRENAL INSUFFICIENCY	ADRENAL INSUFFICIENCY HYPOTHALAMIC PITUITARY ADRENAL AXIS SUPPRESSION SECONDARY ADRENOCORTICAL INSUFFICIENCY
DIABETES MELLITUS	DIABETES MELLITUS DIABETIC KETOACIDOSIS FULMINANT TYPE 1 DIABETES MELLITUS LATENT AUTOIMMUNE DIABETES IN ADULTS TYPE 1 DIABETES MELLITUS
DIARRHEA/COLITIS	AUTOIMMUNE COLITIS COLITIS COLITIS ULCERATIVE DIARRHOEA ENTERITIS ENTEROCOLITIS
HEPATITIS	ACUTE HEPATIC FAILURE ACUTE ON CHRONIC LIVER FAILURE ALANINE AMINOTRANSFERASE INCREASED ASPARTATE AMINOTRANSFERASE INCREASED AUTOIMMUNE HEPATITIS BLOOD BILIRUBIN INCREASED DRUG-INDUCED LIVER INJURY HEPATIC FAILURE HEPATITIS HEPATITIS ACUTE HEPATOTOXICITY HYPERBILIRUBINAEMIA TRANSAMINASES INCREASED
HYPERSENSITIVITY	ANAPHYLACTIC REACTION ANAPHYLACTIC SHOCK HYPERSENSITIVITY INFUSION RELATED REACTION

Immune-Mediated Adverse Event Definition

Category	Preferred Terms
HYPERTHYROIDISM	BASEDOW'S DISEASE HYPERTHYROIDISM PRIMARY HYPERTHYROIDISM
HYPOPHYSITIS	HYPOPHYSITIS HYPOPITUITARISM LYMPHOCYTIC HYPOPHYSITIS
HYPOTHYROIDISM	AUTOIMMUNE HYPOTHYROIDISM HYPOTHYROIDISM PRIMARY HYPOTHYROIDISM
HYPOTHYROIDISM/THYROIDITIS	ATROPHIC THYROIDITIS AUTOIMMUNE HYPOTHYROIDISM AUTOIMMUNE THYROIDITIS HYPOTHYROIDISM PRIMARY HYPOTHYROIDISM THYROIDITIS THYROIDITIS ACUTE
NEPHRITIS AND RENAL DYSFUNCTION	ACUTE KIDNEY INJURY AUTOIMMUNE NEPHRITIS BLOOD CREATININE INCREASED CREATININE RENAL CLEARANCE DECREASED HYPERCREATININAEMIA NEPHRITIS NEPHRITIS ALLERGIC PARANEOPLASTIC GLOMERULONEPHRITIS RENAL FAILURE RENAL TUBULAR NECROSIS TUBULOINTERSTITIAL NEPHRITIS
PNEUMONITIS	INTERSTITIAL LUNG DISEASE PNEUMONITIS
RASH	AUTOIMMUNE DERMATITIS

Immune-Mediated Adverse Event Definition

Category	Preferred Terms
RASH	DERMATITIS DERMATITIS ALLERGIC DERMATITIS EXFOLIATIVE DRUG ERUPTION ERYTHEMA MULTIFORME EXFOLIATIVE RASH FIXED DRUG ERUPTION NODULAR RASH RASH RASH ERYTHEMATOUS RASH GENERALISED RASH MACULAR RASH MACULO-PAPULAR RASH MORBILLIFORM RASH PAPULAR RASH PRURITIC RASH VESICULAR STEVENS-JOHNSON SYNDROME TOXIC EPIDERMAL NECROLYSIS TOXIC SKIN ERUPTION
THYROIDITIS	ATROPHIC THYROIDITIS AUTOIMMUNE THYROIDITIS THYROIDITIS THYROIDITIS ACUTE

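### The protocol commits to tabulating immune-related AEs by time point; SAP 7.7.5 plans only pooled 90-day summaries and gives no reason

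*SAP*

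**What the plan says.** Protocol 10.3.1 has all AEs tabulated by system organ class, preferred term, treatment and overall. For one class of event it goes further: "Immune-related AEs will be listed and tabulated by system organ class, preferred term, treatment, overall and time points".

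SAP 7.7 carries over the general AE commitment. For immune-mediated AEs (IMAEs), SAP 7.7.5 says: "IMAEs will be summarized by treatment group for each immune mediated category / PT using the 90-day safety window". Three kinds of summary follow:

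- AEs on the preferred-term list, "without requirement of either usage of immune modulating medications or accounting for immune mediated etiology or immune mediated component";
- IMAEs "where immune modulating medication was initiated presented by Category / PT";
- endocrine IMAEs.

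None is split by time. SAP 6.1 treats Day 1 to about Day 90 as a single on-treatment period. Under SAP 7.7, a participant whose AE has several intensities within a period contributes only the worst grade.

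The kidney terms in SAP Appendix 2 begin "ACUTE KIDNEY INJURY AUTOIMMUNE NEPHRITIS BLOOD CREATININE INCREASED" and go on to renal failure and tubular necrosis. The hepatitis category includes raised ALT, AST and bilirubin and hepatic failure.

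**The concern.** A tabulation that the protocol specifies is missing from the SAP, and it concerns part of the primary safety endpoint (Protocol Section 4, SAP 4.1). The time dimension looks deliberate, because Protocol 10.3.1 adds it for immune-related AEs and not for AEs in general.

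It matters more here than in an oncology trial. Acute kidney injury is one of three organ-dysfunction criteria for entry (Protocol 6.1), and new or worsening kidney or liver dysfunction is also how sepsis progresses. Both arms receive nivolumab, so there is no untreated rate for comparison. In the unfiltered summary, a creatinine rise on Day 3 and one on Day 60 fall in the same cell. The table cannot show when the events it counts began.

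**Working it through.** **1. The plan's own figure.** SAP Section 5 states an 80% probability of seeing at least one AE of 10% incidence with 15 participants. Check: 1 − 0.9^15 = 0.794. It reproduces and is not in dispute.

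**2. The documents side by side.**

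| Data | Time split in protocol | Time split in SAP |
|---|---|---|
| All AEs | None (10.3.1) | None (7.7) |
| Immune-related AEs | By time point (10.3.1) | None; one 90-day window (7.7.5) |
| Laboratory values | Not specified (10.3.1) | By scheduled visit week (7.7.6.2) |
| Exploratory efficacy | Assessed during index hospitalization (9.1) | Periodic time points (7.6.1) |

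No other SAP section in the public text restores the immune-related tabulation. The Amendment 01 summary, in the protocol's document history and in SAP 2.4, does not mention dropping it.

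**3. Which summaries are affected.**

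- *Unfiltered listed terms:* fully affected. Kidney and liver terms enter whatever their cause.
- *Medication-filtered IMAEs:* partly protected. However, Protocol 7.8.1 permits adrenal replacement steroids for septic shock, and SAP 7.7.5 does not say whether starting these counts as initiating immune-modulating medication.
- *Endocrine IMAEs:* contain no kidney or liver terms, so this mixing does not arise.

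The SAP ties its etiology criterion to recent immune-oncology studies: "For these studies, an additional criteria accounting for immune mediated etiology or immune mediated component is also to be considered". It does not say whether that covers this sepsis trial. Protocol 9.2.1, by contrast, defines immune-mediated AEs as those "for which non-inflammatory etiologies (e.g. infection or tumor progression) have been ruled out".

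**4. How far one cell can mix (assumed rates; the documents give none).** Take one category in a 15-participant arm. Let pE be the probability of an early event and pL = 0.10 that of a late one. Assume independence, full follow-up and each participant counted once.

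- Pooled probability: P = 1 − (1 − pE)(1 − pL)
- Expected count: 15 × P
- Share of counted participants with a late event: pL / P
- Expected participants with both, entered once: 15 × pE × pL

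| pE | P | Expected of 15 | Share with a late event | Expected with both |
|---|---|---|---|---|
| 0.10 | 1 − 0.9 × 0.9 = 0.19 | 2.85 | 53% | 0.15 |
| 0.20 | 1 − 0.8 × 0.9 = 0.28 | 4.2 | 36% | 0.30 |
| 0.40 | 1 − 0.6 × 0.9 = 0.46 | 6.9 | 22% | 0.60 |
| 0.60 | 1 − 0.4 × 0.9 = 0.64 | 9.6 | 16% | 0.90 |

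The more early events there are, the less the pooled cell says about late ones.

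**5. The worst-grade rule.** A participant with an early severe event and a later milder one of the same term gives one entry, at the early grade. The later event leaves no trace in the table.

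**The case against.** The strongest reply is that timing and origin are handled elsewhere. Investigators must assess every AE for an immune-mediated mechanism, with extra case report form data for potential cases (Protocol 9.2.2). AEs are summarized by relationship and all are listed (SAP 7.7). Creatinine, ALT, AST and bilirubin are summarized by visit (SAP 7.7.6.2), SOFA scores are summarized over time (SAP 7.6.1), and potential drug-induced liver injury is tabulated (SAP 7.7.6.3). An AE must be new or worsening (Protocol Appendix 3), so stable kidney injury at entry is not counted. With about 30 participants, listings can be read case by case, and their content sits in a Data Presentation Plan outside these documents, so one cannot assume that onset day will be absent. The protocol also leaves its time points undefined.

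Most of this stands, and it limits the consequence. A reader might infer that septic and immune-mediated kidney or liver events cannot be told apart in the safety tables. The documents do not support that: one of the three kinds of summary is unfiltered, one has a medication filter, one is endocrine only, and the laboratory tables and listings give some timing. Nor would a time split settle the question. The documents give no onset window for either cause; a late event can be septic and an early one immune-mediated.

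A reader might also infer that pooling hides a late event altogether. It does so only where the participant is already counted for the same entry. Otherwise the event adds to the count and only its timing is lost.

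The reply does not restore the missing tabulation. Laboratory tables by visit do not count IMAEs and do not cover pneumonitis, colitis or rash. Listings are not the table that the protocol specifies.

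**Conclusion.** The departure from Protocol 10.3.1 is real, unexplained and concerns part of a primary safety endpoint. Its practical effect is moderate and falls mainly on the unfiltered summary, where early sepsis-type organ events and later ones share cells and two events in one participant can become one. The existing safeguards mitigate this in part.

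The mismatch itself rests on the text alone. The size does not: the 53% to 16% range depends on the assumed 10% late rate, the assumed early rates, independence and full follow-up, and is only an illustration. The study is descriptive, so no power or error rate is affected. Adding the table is a worthwhile, inexpensive correction; the omission does not invalidate the safety analysis.

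**What to change.** Add one table to SAP 7.7.5: the unfiltered listed-term AEs by prespecified onset interval, by treatment and total. Days 1-7, 8-28, 29-56 and 57-90 would fit the visit schedule in Protocol Section 2; other cut-points would also serve. Add the medication-filtered IMAEs if wanted. The endocrine summaries need no split for this purpose.

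- Use participants alive and in follow-up at the start of each interval as the denominator.
- Count a participant in every interval in which an event begins, so that an early and a late event both appear.
- Show onset day in the IMAE listing.
- Fix the intervals in the SAP before the tables are produced, since sponsor staff are unblinded during the trial (SAP 2.3).

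If the sponsor prefers to keep only pooled summaries, the SAP should give its reason for departing from Protocol 10.3.1. That would close the documentary gap but leave the mixing in place.

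Cost: one additional table from AE onset dates, with 4 intervals × (2 arms + total) = 12 columns and many cells of 0 or 1. No new data collection is needed, because AEs are already collected to Day 90.

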## **7.8 Concomitant Therapy**

### **7.8.1 Prohibited and/or Restricted Treatments**

Prohibited and/or restricted medications taken prior to study treatment administration or during the study are described below. Medications administered during the index hospitalization within

1 week prior to study treatment administration must be recorded on the CRF. Any concomitant therapies must be recorded on the CRF.

- 1) During the study, immunosuppressive agents are prohibited unless utilized to treat a drug related adverse event. **NOTE:** Adrenal replacement steroid doses up to the equivalent of hydrocortisone 300 mg/day for the treatment of septic shock are permitted.

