4 ENDPOINTS

4.1 Primary Endpoint

The primary objective (to assess the safety and tolerability) will be measured by the incidence rates of AEs, SAEs, AEs leading to discontinuation, immune-mediated AEs, and deaths. In addition, clinical laboratory tests, vital signs, and ECGs will be summarized.

The primary objective (to assess the pharmacokinetics of BMS-936558) will be measured by the following PK endpoints.

C_{\max}	Peak nivolumab serum concentration
C_{\min}	Trough nivolumab serum concentration
C_{avg}	Average nivolumab serum concentration
T_{\max}	Time of maximum observed concentration
CLT	Total clearance
V_d	Volume of distribution
$T_{1/2}$	Half-life
$AUC(0-T)$	Area under the serum concentration-time curve from time zero to time of last quantifiable concentration

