5 SAMPLE SIZE AND POWER

The number of participants is not based on statistical power consideration. Administration of nivolumab to up to approximately 15 participants in each arm provides an 80% probability of observing at least one occurrence of any adverse event that would occur with $\geq 10\%$ incidence in the population from which the sample is drawn.

The overall purpose of Study CA209923 is to evaluate the safety, tolerability, pharmacokinetics, and pharmacodynamics of two single doses of nivolumab in participants with severe sepsis or septic shock in order to inform feasibility and conduct of further studies of nivolumab in this population. Specifically, a key objective is to determine whether the exposures observed after a single dose of nivolumab in participants with severe sepsis or septic shock are comparable to the overall exposures observed at steady-state dosing with the nivolumab regimen approved in oncology indications. In order to achieve this goal, up to 15 subjects per dose level are estimated in order to obtain a PK profile from at least 6 subjects per dose level.

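### The SAP's immune-mediated AE rule does not separate steroid given for septic shock from steroid given for the event, so its medication table can count septic organ events that the protocol's own definition would exclude

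*SAP*

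**What the plan says.** SAP 4.1 measures the primary safety objective by "incidence rates of AEs, SAEs, AEs leading to discontinuation, immune-mediated AEs, and deaths".

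SAP 7.7.5 builds the IMAE from a list of preferred terms, a 90-day window after the dose, no causality requirement and, for non-endocrine events, a medication condition: "treated with immune-modulating medication (of note, endocrine Adverse events such as adrenal insufficiency". It adds a further criterion (no other clear cause in the investigator's judgement, or an immune component) but introduces it for recent immune-oncology studies. Three sets of summaries follow. The first takes every listed term and expressly waives both the medication and the cause conditions. The second is restricted to IMAEs "where immune modulating medication was initiated presented by Category / PT". The third is for endocrine IMAEs.

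The term list in SAP Appendix 2 includes "ACUTE KIDNEY INJURY AUTOIMMUNE NEPHRITIS BLOOD CREATININE INCREASED", together with renal failure, hepatic failure, raised ALT, AST and bilirubin, and diarrhoea.

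Protocol 7.8.1 bans immunosuppressive agents except to treat a drug-related event, with this note: "Adrenal replacement steroid doses up to the equivalent of hydrocortisone 300 mg/day for the treatment of septic shock are permitted".

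Protocol 9.2.1 treats an AE as immune-mediated only when causes such as infection have been ruled out, while allowing events with another cause that autoimmunity made worse. Protocol 9.2.2 has the investigator judge every AE on this question.

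**The concern.** In oncology, a newly started steroid is a reasonable marker that someone was treating an immune reaction. Here the same drug class may be started for the disease under study. Protocol 3.3 names corticosteroids as the usual treatment for high-grade immune-mediated events, and Protocol 7.8.1 permits them for shock, so a flag based on drug class alone cannot tell the two uses apart. The listed kidney, liver and gut terms are ones that sepsis itself can produce; acute kidney injury is even a qualifying organ dysfunction in Protocol 6.1.

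At stake is the meaning of a primary safety count. The protocol and the SAP give it two different definitions, and two programmers could derive different numbers from the same data. With about 15 participants per arm, each misclassified participant moves an arm's rate by 1/15 = 6.7 percentage points.

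**Working it through.** **1. Inputs from the documents.** Arm size: up to about 15 (SAP 5). IMAE rule: SAP 7.7.5. Term list: SAP Appendix 2. Permitted steroid: Protocol 7.8.1. Protocol definition and data source: Protocol 9.2.1 and 9.2.2. Neither document gives a rate of shock-steroid use or of the listed events.

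**2. The plan's own figure.** SAP 5 states: "Administration of nivolumab to up to approximately 15 participants in each arm provides an 80% probability of observing at least one occurrence" of an AE with at least 10% incidence. Check: 1 − (1 − 0.10)^15 = 1 − 0.9^15 = 0.794, which agrees with 80%. The point does not depend on this figure; it only confirms the arm size.

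**3. One case under each text.** Suppose a participant develops worsening acute kidney injury after dosing, the investigator judges it due to sepsis, and hydrocortisone is started for shock a day later.

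| Text applied | Counted as immune-mediated? |
|---|---|
| SAP 7.7.5 medication table, read literally (listed term, 90 days, medication initiated) | Yes |
| SAP 7.7.5 definition, if the medication must have treated that event | No |
| SAP 7.7.5 with the alternate-cause criterion applied | No |
| Protocol 9.2.1 | No |

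The SAP does not say which of the first three rows governs. It has no list of immune-modulating medications and no rule on indication, dose, start date or link to the event. SAP 7.5.2 also refers to immune-modulating medication without defining it. In this case the steroid starts after the event, so a start-date rule alone would not exclude it; the reason for giving it, or the investigator's assessment, is also needed.

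**4. Illustration of size (assumed inputs).** Let s be the share starting shock steroid after dosing and a the share with a listed kidney, liver or gut AE, assumed independent. The coincidental share is q = s × a, the expected number per arm is 15q, and the chance of at least one is 1 − (1 − q)^15.

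- s = 0.20, a = 0.20: q = 0.04; 15q = 0.6; 1 − 0.96^15 = 0.458
- s = 0.40, a = 0.35: q = 0.14; 15q = 2.1; 1 − 0.86^15 = 0.896
- s = 0.60, a = 0.50: q = 0.30; 15q = 4.5; 1 − 0.70^15 = 0.995

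These figures apply only to the literal reading. They ignore the order of steroid and event, and they assume no cause filter; both make them upper-side values. If steroid use and organ events both follow sepsis severity, independence errs the other way.

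**The case against.** The strongest reply is that the definition already protects the count. It requires the event to have been treated with the medication, and the reason given for the endocrine exception (such reactions are often managed without it) supports an event-linked reading. The medication table summarises IMAEs, so its label may only narrow a defined term. The word *initiated* may also exclude steroid already running. Because the first table alone waives both medication and cause, the later tables may be meant to apply both. The passage on events that the investigator considers potentially immune-mediated might cover every category. This trial does collect the assessment on which the cause criterion depends, so the immune-oncology wording could simply be template text. Further conventions sit in internal documents that are not available here.

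These are fair readings, and they limit the claim to what the text permits. None is stated, and the one criterion that would match Protocol 9.2.1 is worded for another class of study.

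Three stronger inferences are tempting but unsupported:

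- **That the endocrine table is affected in the same way.** It has no medication condition for hydrocortisone to satisfy, and permitted replacement steroid does not by itself create an adrenal AE; a new or worsened condition must be reported (Protocol Appendix 3).
- **That miscounted events would be attributed to nivolumab.** The rule disregards causality, and drug-related AEs and SAEs are tabulated separately. The harm is misclassification under the immune-mediated label.
- **That a chance imbalance in steroid use would pass as a dose effect.** No between-dose test of IMAEs is planned, and concomitant medications are summarised by arm, so an imbalance could be seen.

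**Conclusion.** The point holds as a statement of what SAP 7.7.5 allows, not of what will happen. Read literally, the medication table can count septic kidney, liver or gut events that coincide with permitted shock steroid, contrary to Protocol 9.2.1. This is more than missing detail, because it leaves a primary safety endpoint with two definitions.

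The size is unknown. The range of 4% to 30% (0.6 to 4.5 of 15 per arm) follows entirely from assumed rates, independence and the loosest reading, and should not be quoted as an estimate. Both arms receive nivolumab, so no arm shows the background rate; that is a feature of the design which clearer wording would not change.

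**What to change.** Amend SAP 7.7.5. This concerns the analysis definition only and implies no change to steroid management.

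1. State that the criterion of no other clear cause, or an immune component, applies to this study's IMAE tables, using the investigator assessment collected under Protocol 9.2.2. The SAP then matches Protocol 9.2.1.
2. Count a medication only if it was started or increased on or after onset of the listed event and was given for that event. Use the recorded indication if the CRF has one; the documents show that medications are recorded but do not mention an indication field. Otherwise use the start date together with the investigator assessment.
3. State that steroid given for septic shock under Protocol 7.8.1 does not satisfy the medication condition.
4. Keep the existing unfiltered table of listed terms as the sensitivity view, so that nothing is hidden by the narrower rule.

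The cost is SAP wording and modest programming. The downsides are a departure from the sponsor's standard IMAE programming and some reliance on investigator judgement.
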